3. OBJECTIVES

3.1 Primary Objectives

3.1.1 Performance of Algorithm to Predict Decrease in Lymphocyte Count Post-SBRT

Determine if the lymphodepletion predictive algorithm developed by UVA coupled with the existing optimization algorithm in radiation treatment planning software predicts the magnitude of lymphocyte depletion in a prospective cohort of patients treated with lung SBRT.

Hypothesis: We hypothesize that our predictive algorithm, which estimates risk of post-SBRT lymphopenia based upon estimation of radiation dose to blood vessels, can accurately predict change in lymphocyte count at 4 weeks following SBRT in a prospective cohort of lung SBRT patients.

Endpoint: After randomization and completion of treatment planning, the algorithm will predict the decrease in lymphocyte count for each participant (in Arms A and B) at 4 weeks after SBRT. The predicted decrease will be compared with the actual decrease in lymphocyte count observed.

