3.1.2 Impact of Lymphocyte-Sparing SBRT Planning Objectives on Post-SBRT Lymphocyte Count

Determine if lymphocyte-sparing SBRT planning (Arm A, investigational) results in less *in vivo* lymphocyte depletion compared to controls who receive standard SBRT planning (Arm B, control).

Hypothesis: We hypothesize that we can generate treatment plans that both meet standard of care objectives for organs-at-risk (OAR) and result in a smaller reduction in lymphocyte count by reducing exposure of circulating lymphocytes in great vessels.

Endpoint: Observed changes in lymphocyte count from baseline and 4 weeks after completion of lung SBRT for participants in each arm. Expected lymphocyte nadir time point of 4 weeks following SBRT will be used to assess changes in lymphocyte counts in each arm.

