3.2.2 Performance of Algorithm to Predict Decrease in Lymphocyte Count Post-SBRT

Determine if our lymphodepletion predictive algorithm coupled with the existing optimization algorithm in radiation treatment planning software predicts the magnitude and trajectory of lymphocyte depletion in a prospective cohort of patients treated with lung SBRT.

Hypothesis: We hypothesize that our predictive algorithm, which estimates risk and magnitude of post-SBRT decrease in lymphocyte count based upon estimation of radiation dose to blood vessels, can accurately predict the time course of changes in lymphocyte counts in a prospective cohort of lung SBRT patients.

Endpoint: After randomization and completion of treatment planning, the algorithm will predict the decrease in lymphocyte count for each participant (in Arms A and B) for each follow-up time point (at end of SBRT, and 4 weeks and 6 months after SBRT). The predicted time course of lymphocyte count will be compared with the actual decrease in lymphocyte count observed.

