5. STATISTICAL CONSIDERATIONS

Study populations Any participant who initiates either standard or optimized SBRT will be considered evaluable for adverse events. Participants with observed changes in lymphocyte counts at any of the follow-up times will be considered evaluable for the analyses of changes in lymphocyte counts.

Randomization and stratification

[figure not shown]
Participants will be randomized to standard or optimized SBRT in a 1:1 ratio using randomly permuted blocks. Block sizes of 2 or 4 will be randomly chosen with equal probability. The randomization will be stratified by central or peripheral lung lesion (section 4.1.1)

Sample size and power The first aim is to compare the actual and predicted values from the simulations. We will calculate the empirical distribution function of the difference between predicted and actual, both in terms of lymphocyte counts and percent change from pretreatment counts. Current simulation is able to predict to 17% accuracy, with a standard deviation of 15%. The model will be considered an improvement if 80% of the predictions are within 10% of the actual counts or percent changes. With a sample of size 50 evaluable, the one-sample t-test has 95% power, with a one-sided significance level of 5%, for testing whether the mean percent difference is less than 17%, when the true mean is 10%.

The second aim is to compare standard versus optimized SBRT on the basis of the primary outcome, lymphocyte drop at 4 weeks. The sample size was chosen to have sufficient power for comparing the groups using a repeated measures model for comparing the groups. Estimates of effect sizes and variation were based on repeated measures models, with change points at 4 and 12 weeks, fit to retrospective data on lymphocyte drop within 24 weeks following standard SBRT. A spatial-power model was used for the covariance matrix of percentage changes from baseline in lymphocyte counts,

yielding an estimated standard deviation of 10.5 percentage points and a within-subjects correlation estimate of 0.40 for observations taken 1 week apart. The fitted model, overlaid on the individual patient profiles is displayed above.

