For the second aim, repeated measures models will be used to compare the groups with respect to the percentage drop in lymphocyte counts. The stratification factor will be used as a covariate in the model. Contrasts will be used to compare the groups at specific time points, including the 4 week post-treatment time point, where we anticipate there will be the greatest difference between the standard and optimized SBRT groups. The sample size was based on an assumed spatial power covariance structure, but we will consider other covariance matrices as well, such as random effects models. In exploratory analyses will tabulate local control as well as adverse events (see *section 8*) and estimate differences these between groups. Kaplan–Meier curves will be used to summarize overall survival in each of the standard and optimized SBRT groups.

Quantitative analysis of blood counts and radiation dose to the great vessels

We will collect blood, serum and PBMC at baseline and at end of treatment, weeks 4, and 24 after treatment for all study patients. The reference point for post-treatment blood collection will be the start date of radiation therapy to permit intergroup comparisons between the two study arms. This comparison framework was selected based on our available preliminary data, which

suggests that RT-induced lymphocyte effects occur as early as one week following radiation initiation due to the high radiosensitivity of circulating lymphocytes. We will quantify absolute neutrophils, hemoglobin, platelet, and lymphocyte counts for all patients at these time points and compare the changes between the groups and also compare the lymphocyte count results to what was predicted by the simulation algorithm. We will perform a multivariate analysis to identify the correlation between TRL and mean/integral radiation dose to the great vessels. Since substantial circulating blood is also present in the heart and lungs we will also correlate mean heart and lung dose with TRL. Measurement of the magnitude of lymphocyte depletion and correlation with great vessel, lung, and heart integral dose will be performed and compared to the predicted levels for the simulation algorithm.

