7.1.4 Dose Fractionation

Participants on both Arm A and Arm B will receive 50-60 Gy in 5 fractions to the PTV. Treatments should be delivered within 5-10 business days (excluding the weekend(s) and holidays when the clinic is closed).

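### Section 5 counts post-treatment blood draws from the start of radiation while the primary endpoints and calendar count from SBRT or its completion, and it promises PBMC and serum at two visits with no research blood scheduled

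*Combined protocol and SAP*

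**What the plan says.** **Clock.** In Section 5, under the quantitative analysis of blood counts, the plan lists blood, serum and PBMC at baseline, end of treatment, and weeks 4 and 24 after treatment. The next sentence says: "The reference point for post-treatment blood collection will be the start date of radiation therapy". It gives two reasons: to allow comparison between the arms, and preliminary data which "suggests that RT-induced lymphocyte effects occur as early as one week following radiation initiation".

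Other places count differently:
- Section 3.1.1: "the algorithm will predict the decrease in lymphocyte count for each participant (in Arms A and B) at 4 weeks after SBRT".
- Section 3.1.2: "Observed changes in lymphocyte count from baseline and 4 weeks after completion of lung SBRT for participants in each arm".
- Section 5, second aim: "Contrasts will be used to compare the groups at specific time points, including the 4 week post-treatment time point".
- Section 9: a column for completion of SBRT, then a draw at 4 weeks +/- 2 weeks and one at 6 to 9 months, both following SBRT.
- Sections 8.1.2 and 8.2: CBC and research blood are collected as the Section 9 calendar sets out.

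On course length, Section 7.1.4 says: "Treatments should be delivered within 5-10 business days".

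**PBMC and serum.** Section 3.2.3 and Table 1 promise PBMC at baseline, end of SBRT, 4 weeks and 6 months. Section 8.3.3 compares antibody titers at several times after radiation with baseline. Section 8.2 and the research-blood row of Section 9 provide two draws only: before SBRT and about 4 weeks after.

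**The concern.** Both primary aims rest on one lymphocyte count, taken at the time when the plan expects the nadir. Aim 1 compares that count with a prediction made for 4 weeks after SBRT. Aim 2 compares the arms on it. If the nadir is 4 weeks after completion, a count drawn 4 weeks from the start of radiation comes before it. That shrinks the difference between arms and charges a timing error to the algorithm. The calendar window would not catch this, because day 15-24 after completion lies within its day 14-42.

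The second conflict is separate. Part of a secondary endpoint relies on samples that no visit collects.

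**Working it through.** **1. Distance between the clocks.** From first to last fraction, ignoring holidays, 5 business days span 4-6 calendar days and 10 span 11-13, depending on the weekday of the start. Day 28 from the start is therefore day 28 - 13 = 15 to day 28 - 4 = 24 after completion.

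**2. The plan's own figure.** Section 5 gives more than 99% power for the 4-week contrast, with 25 per arm, SD 10.5 points, effect parameter 0.60 and two-sided 5%. The historical mean profile is shown only in a figure, so this cannot be reproduced directly. Solving backwards:
- SE = 10.5 x sqrt(2/25) = 2.97.
- 99% power (t, 48 df) needs a contrast of 12.99 points.
- Under the plan's model the contrast is 0.60 x the control drop, so the drop is at least 12.99/0.60 = 21.7 points.

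**3. Start-date sentence followed, draw exactly on day 28 from the start, nadir 28 days after completion.** Let s be the span in days and f the share of the nadir drop reached at the draw. Three assumed shapes:
- A, linear fall beginning at completion: f = (28 - s)/28.
- B, linear fall beginning at the start of radiation: f = 28/(28 + s).
- C, half the fall reached by completion: f = 0.5 + 0.5(28 - s)/28.

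Over s = 4 to 13, f runs 0.857-0.536 (A), 0.875-0.683 (B) and 0.929-0.768 (C). With spans spread evenly, mean f is 0.696, 0.772 and 0.848.

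Worked case, shape A: contrast = 12.99 x 0.696 = 9.05. The variance of f is 8.25/28² = 0.0105. Spans then add 21.66² x 0.0105 = 4.9 to the control variance and (0.4 x 21.66)² x 0.0105 = 0.8 to the optimized-arm variance, an average of 2.9. So SD = sqrt(110.25 + 2.9) = 10.64, SE = 3.01 and power = 84%.

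| Control drop | Power A | Power B | Power C |
|---|---|---|---|
| 21.7 points | 84% | 91% | 95% |
| 25 points | 92% | 97% | 99% |
| 30 points | 98% | 99.5% | 99.9% |

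**4. Aim 1, same draws.** Read the rule as 80% of predictions within 10 percentage points. An algorithm that exactly meets it has error SD = 10/1.2816 = 7.80. An early draw shifts the error by b = drop x (1 - f) in the control arm and 0.4 times that in the optimized arm. The score is Φ((10 - b)/7.80) - Φ((-10 - b)/7.80), averaged over spans and arms. For example, in the control arm with s = 13 and shape A, b = 21.66 x 0.464 = 10.06 and the score is 0.497 - 0.005 = 49%. The averages at 21.7 points are 71%, 75% and 78%. At 30 points the same formula gives 64%, 70% and 75%, so a larger drop protects Aim 2 but not Aim 1. For scale, the binomial SE at n = 50 is sqrt(0.8 x 0.2/50) = 5.7 points.

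**5. The opposite case: planning clock from the start of radiation.** The nadir is then day 28 from the start, and a start-date draw loses nothing. A draw 4 weeks after completion comes s days after the nadir. If a share r of the drop has recovered by week 12, f = 1 - r x s/56. Power at the 21.7-point drop is 99% for r = 0. For r = 1, mean f = 0.848 and power is 95%.

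**6. Late visit.** 6 months is 6 x 30.44/7 = 26.1 weeks and 9 months is 39.1 weeks. The window opens after week 24. It also lies beyond the planning data, described as "with change points at 4 and 12 weeks, fit to retrospective data on lymphocyte drop within 24 weeks following standard SBRT".

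**7. Samples promised and scheduled.**

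| Visit | PBMC promised (3.2.3, Table 1, Section 5) | Research blood (8.2, 9) | CBC (9) |
|---|---|---|---|
| Baseline | yes | yes | yes |
| End of SBRT | yes | no | yes |
| About 4 weeks | yes | yes | yes |
| 6 months/week 24 | yes | no | yes |

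Section 5 promises serum at the same four times.

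**The case against.** The strongest reply is that the documents already say what governs collection. Sections 8.1.2 and 8.2 defer to the calendar, and the sentence just before the disputed one says after treatment. On that reading the start-date line is a stray remark, and staff who follow the calendar draw at the right time. This stands, and it is why the losses above are conditional.

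A reader might go further and infer that every 4-week count will be 4-13 days early. The documents do not support that. It holds only for a draw exactly on day 28 from the start. If the calendar's +/- 2 weeks were applied to the start date, draws would fall on days 14-42 from the start, which is day 1-38 after completion, so some would come after the target.

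The size is also open to challenge. The 84% is the worst of three shapes at the minimum drop. The anchor is not secure either: a 12.99-point contrast alone would give a 2-3 df F-test about 96%-98% power, yet Section 5 states 80% for the F-test on the same profile. The start-date sentence is tied to preliminary data, so the planning clock may itself have run from the start (step 5). The endpoint wording and the description of the planning data favour completion, but Section 5 admits uncertainty about when the maximum drop occurs.

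A further tempting inference is that the wide windows, with no rule on actual or nominal draw times, undermine the analysis. On the assumed profiles, the 4-week window alone, counted from completion, leaves power at 93%-97% with draws uniform over weeks 2-6, or 97%-98% with draws centred on day 28. It moves the Aim 1 score to 75%-78% or 78%-79%, within one binomial SE of 80%. No bias between arms is built in.

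**Conclusion.** Two textual conflicts stand and should be fixed.

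First, the start-date sentence contradicts the primary endpoints and the calendar by 4-13 days. If the calendar is followed, the cost is nil. If the sentence is followed and the nadir is 4 weeks after completion, 4-week power is 84%-95% at the minimum drop and close to the stated figure at 30 points, and Aim 1 could fail its 80% rule because of the clock alone. These figures rest on assumed profiles, evenly spread spans and draws exactly on day 28. They illustrate what is at stake and do not predict a loss. Confidence is high in the conflict and much lower in its size.

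Second, the PBMC part of secondary endpoint 3.2.3 cannot be produced at end of SBRT or at 6 months under the current schedule, and the serum collection in Section 5 has the same problem. A reader might take this to threaten the lymphocyte-count endpoints. It does not, because those come from the CBC.

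The lack of a rule on actual or nominal draw times is missing detail and does not carry the point.

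**What to change.** 1. Replace the start-date sentence so that post-treatment draws and analysis times count from completion of SBRT, as in Section 3.1.2. Record the start, completion and draw dates. The plan's two reasons are still met: early effects are covered by the CBC within 3 days after completion (Section 9, footnote 4), and both arms follow the same 5-10 business-day schedule.
2. Reconcile the PBMC and serum passages with the schedule. The route without extra cost is to limit the PBMC part of 3.2.3, its Table 1 entry, the PBMC and serum collection in Section 5 and the titer comparison in 8.3.3 to baseline and 4 weeks, with CBC counts at the other visits. Scheduling the missing draws is the alternative, and the choice is the sponsor's.
3. Relabel the week-24 visit in Section 5 as 6-9 months.

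Optional: state whether actual or nominal days enter the model, and add a sensitivity analysis by draw day. For Aim 1, Section 3.2.2 already foresees a predicted time course ("The predicted time course of lymphocyte count will be compared with the actual decrease in lymphocyte count observed"), so comparing at the actual draw day may be possible.

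Cost: minor wording changes, a narrower PBMC endpoint if the first route is taken, and a check that the dates are in the database, which the documents do not state. No visits or samples are added.

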6. REGISTRATION PROCEDURES

Participants cannot be registered until institutional IRB approval of the protocol and consent are obtained. Registration and randomization should occur around the time of planning CT (+/- 5 business days). SBRT must begin within 4 weeks after registration/randomization.

6.1 Patient Registration & Randomization

All participants must sign the consent form prior to determination of eligibility for this study. Patients will be screened and evaluated to meet all eligibility criteria before being registered on the trial. Once a patient is determined to be eligible for the study, study staff will register the patient in the UVA Cancer Center OnCore database in accordance with the Clinical Trial Management System Policy, via the UVA OnCore Resources link in Oncore. Participants will be associated with a UVA unique identifier, such as UVA SBRT-001, that will represent the participant in the study. This will be listed as the participant's sequence number in the OnCore database and will be on all research blood samples collected from participants.

Randomization will be discussed with participants during the process of informed consent and informed consent must be documented prior to randomization. Participants will be randomized 1:1 to Arm A or Arm B using randomly permuted blocks, with block sizes of 2 or 4 randomly chosen with equal probability. Stratification is described below. Randomization will be performed using custom randomization software (RAND) that incorporates the randomization scheme generated by the study statistician. Clinical research staff and treating clinicians will be aware of arm assignment and participants may be made aware of their arm assignment. The labels on research blood will not include the treatment arm on which the participant is assigned and this information will not be provided to lab investigators and staff.

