Patients who decline surgery or are considered to be medically inoperable with (American Joint Committee on Cancer (AJCC) edition 8 clinical stage NSCLC lung cancer that are clinically node negative by positron emission tomography computed tomography (PET CT) imaging and have planned treatment with SBRT as definitive therapy.

Phase of Study

Pilot

Study Sites

This is a single site study being conducted at the University of Virginia (UVA).

Intervention

Participants will receive standard of care SBRT using standard technology (treatment planning software and delivery system) that meets all requirements for tumor coverage and sparing of

dose to organs-at-risk. Participants will be randomized to one of two arms, with Arm A participants receiving lung SBRT plans that are also optimized to reduce risk and/or magnitude of decreases in lymphocyte count through reduced treatment of the great vessels beyond standard treatment objectives. Arm B participants will not receive this additional optimization (standard of care).

Study Duration

We expect it will take about 36 months to reach target accrual and data analysis/publication is expected to take an additional 12 months.

Participant Duration

Participants will be assessed prior to SBRT and then will be followed for 6 months following SBRT in order to assess changes in lymphocyte count and lymphocyte subsets. Overall survival will be assessed every 6 months for 1 year following SBRT and then annually. Results from CBC blood tests will also be collected (for participants with results available by standard of care) every 6 months.

Accrual Goal

In order to have 50 evaluable participants, as defined in *section 7.8*, up to 65 participants will be enrolled.

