4.1 Eligibility

4.1.1 Inclusion Criteria

- 1. Willingness and ability to provide written informed consent and to comply with the study protocol.
- Diagnosis of biopsy confirmed non-small cell lung cancer (NSCLC) with planned treatment with SBRT as definitive therapy OR imaging confirmed lung lesion for which SBRT is planned for primary lung cancer (when clinician determines biopsy is not indicated), Registration should occur within 5 business days (before or after) of planning CT.
- 3. Patients must decline surgery or tumor(s) must be considered to be medically inoperable
- 4. Location and size of tumor- Participants must have either:
 - peripherally located tumors (> 2 cm in all directions from the proximal bronchial tree; see Figure 2 above) as defined by RTOG 0915, OR
 - centrally located tumors (tumor size ≤ 5 cm, tumors within or touching the zone of the proximal bronchial tree or adjacent to mediastinal or pericardial pleura) as defined by RTOG 0813.

- 5. Patients with recurrence of prior surgically treated lung cancers are eligible if no further surgery is planned and they otherwise meet the eligibility criteria.
- 6. Measurable disease on chest CT, PET CT, CT simulation at diagnosis (must be within 8 weeks of SBRT).
- 7. Pre- radiation therapy total lymphocyte count > 0.5k/μL on blood count drawn within 2 weeks prior to registration.
- 8. In the opinion of the treating clinician, patient is medically able to tolerate the study SBRT treatment of 50-60 Gy in 5 fractions.
- 9. ECOG performance status of 0-2.
- 10. Age ≥ 18 years.
- 11. If participant is a woman of childbearing potential (WOCBP), agreement to adhere to contraception requirements from the time of consent through completion of SBRT (see section 4.1.3).

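### Printed block sizes of 2 or 4 at a single open-label site make about 53-55% of allocations foreseeable with at least 83% certainty, a selection-bias risk to the Arm A versus Arm B comparison

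*Combined protocol and SAP*

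**What the plan says.** Section 5 (Statistical Considerations, randomization and stratification) states: "Participants will be randomized to standard or optimized SBRT in a 1:1 ratio using randomly permuted blocks". It goes on: "Block sizes of 2 or 4 will be randomly chosen with equal probability". It adds: "The randomization will be stratified by central or peripheral lung lesion". Section 6.1 gives the block sizes a second time, in the text that staff use to register patients: "using randomly permuted blocks, with block sizes of 2 or 4 randomly chosen with equal probability".

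The Synopsis describes a single-site study. On blinding, Section 6.1 says: "Clinical research staff and treating clinicians will be aware of arm assignment and participants may be made aware of their arm assignment". Only laboratory investigators and staff are kept unaware of arm. Assignments come from software loaded with a scheme made by the study statistician, after documented consent and an eligibility check.

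Three provisions bear on discretion at entry:
- Inclusion criterion 8 rests on clinical judgement: "In the opinion of the treating clinician, patient is medically able to tolerate the study SBRT treatment".
- Criterion 7 means that the lymphocyte count is known before registration.
- Criterion 2 and Section 6 put registration within 5 business days either side of the planning CT.

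The documents describe no safeguard against inferring the next assignment from earlier ones, such as undisclosed block sizes or recruiters kept unaware of past assignments.

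**The concern.** The software hides the list, but it cannot hide what follows from published block sizes and a visible history. With blocks this short, a simple rule works: whichever arm is behind in the stratum probably comes next. No calculation is needed to use it.

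Recruiters also hold information that the trial itself treats as relevant to outcome. The Introduction reports that dose to thoracic organs correlates with lymphocyte depletion, and tumour position relative to the vessels is visible on imaging. Someone who expects a given arm could, even without intent, be readier to offer the trial to one patient than to another. The Arm A versus Arm B difference in lymphocyte drop at 4 weeks would then partly reflect who was entered. A laboratory-measured endpoint does not protect against this, because selection acts before anything is measured.

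**Working it through.** The plan states no predictability figure, so there is none to reproduce.

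**Inputs from the documents.** Block sizes 2 or 4, each with probability 1/2; 1:1 ratio; two strata; one site (Synopsis, Sections 5 and 6.1). 50 evaluable; 55 enrolled in Section 5, up to 65 in the Synopsis; about 36 months of accrual. SD of percentage change 10.5 points; 25 per arm (Section 5).

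**Assumption.** The recruiter knows the printed sizes and the past assignments in the stratum, but not the size of the current block.

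**Step 1: one case by hand.** The second patient in a stratum gets the opposite arm with probability 1/2 × 1 + 1/2 × 2/3 = 0.833. Updating the probability of the next arm after each assignment shows that 0.833 is the lowest value whenever the arms are unequal. When they are equal it is 0.50.

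**Step 2: how often the arms are unequal.**
- Block of 2: 1 position.
- Block of 4: 1 + 1/3 + 1 = 7/3 positions.
- Mean per block: (1 + 7/3)/2 = 5/3. Mean block length: 3.
- Long-run share: (5/3)/3 = 5/9 = 55.6%.

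The exact share for one stratum of 25 is 53.5%. For the whole trial, over every central/peripheral split, it is 53.4-55.4% (N = 50), 54.4-54.6% (N = 55) and 54.6-54.8% (N = 65).

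**Step 3: how often the guess is right.** Correct calls at unequal positions average (1 + (2/3 + 1/3 + 1))/2 = 1.5 per block, so these calls are right 1.5/(5/3) = 90% of the time. Over all allocations the rate is (1.5 + 0.5 × (3 − 5/3))/3 = 72.2% (71-72% at this trial's size). About 10-11% of allocations are certain.

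**Step 4: illustrative effect on the test.** Let γ be the shift in expected outcome, in percentage points, in line with the guess, and F the correct-guess rate. Bias = 2γ(2F − 1). SE = 10.5 × √(2/25) = 2.97. With F = 0.72:

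| γ (assumed) | Bias (points) | Bias/SE | Two-sided type I error |
|---|---|---|---|
| 1 | 0.88 | 0.30 | 6% |
| 2 | 1.76 | 0.59 | 9% |
| 3 | 2.64 | 0.89 | 14% |

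A simulation with two strata of 25 and a stratum-adjusted t-test agrees: shifts of 0.1, 0.25 and 0.5 SD (1.05, 2.6 and 5.25 points) give about 6%, 11% and 29%.

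**Step 5: blocks of 4, 6 and 8, with the sizes known to recruiters.**

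| | 2/4 | 4/6/8 |
|---|---|---|
| Callable above 0.80 | 55% | 22% |
| Callable above 0.70 | 55% | 57% |
| Certain | 10% | 2% |
| Correct guesses | 72% | 67% |
| Type I error at γ = 3 | 14% | 11% |
| Mean final arm imbalance, 55 patients | 1.1 | 1.35 |
| 95th percentile of imbalance | 3 | 3 |

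At γ = 3 the bias under 4/6/8 is 2 × 3 × (2 × 0.67 − 1) = 2.04 points, which is 2.04/2.64 = 77% of the bias under 2/4.

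**The case against.** The case against giving this much weight is substantial, and most of it stands.

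- **The size of the shift is assumed.** Nothing in the documents supports any value of γ. At 1 point the error is barely above nominal.
- **Tracking is an inference.** Section 6.1 says that staff and clinicians know arm assignment. It does not say that each recruiter follows the cumulative sequence by stratum.
- **Delay is a narrow route.** At 65 patients over 36 months (1.8 a month) and an assumed even split, about 0.21 same-stratum entries are expected per week. The chance that another entry changes the forecast is about 19% in the week after the planning CT and 34% over the full two-week window. Refusal on tolerance grounds would come after consent. The main open route is whom to offer the trial.
- **The planning CT adds little.** Imaging within 8 weeks of SBRT already shows the anatomy, whether registration comes before or after that scan.
- **Larger blocks look better than they are.** The fall from 55% to 22% depends on the 0.80 cut-off. At 0.70 there is no improvement, and most of the modelled bias remains if the sizes are known.
- **Location is already handled in part.** It is a stratification factor and a covariate in the aim 2 model, so selection would have to act on anatomy within stratum.

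None of this removes the foreseeability itself, which follows from the printed sizes and the open-label, single-site setting. It limits the claim about harm, and it makes concealment matter more than the change of sizes.

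**Conclusion.** The design leaves the second primary aim open to a foreseeable-allocation risk that could readily be avoided. The predictability figures (about 53-55% callable with at least 83% certainty, about 10% certain, about 72% of guesses right) follow exactly from the stated scheme, given a recruiter who knows the printed sizes and follows the sequence. They are expected shares for the whole trial; one small stratum can fall below half (45% for 5 patients). The type I error of 6% to 14% is an illustration over assumed shifts of 1 to 3 points.

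A reader might infer more, and the documents do not support it:
- That allocation has in fact been influenced. Nothing shows this.
- That the whole trial is compromised. The first primary aim compares predicted with observed counts within patients in both arms and does not rest on the randomized contrast.
- That no analysis could help. Adjustment for recorded baseline factors could reduce the bias, though it could not remove selection on unrecorded features.

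This is a sensible improvement at small cost, not a flaw that invalidates the comparison.

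**What to change.** Two changes, made together, for all remaining allocations:

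1. Issue a new list without blocks of 2, for example sizes 4, 6 and 8 chosen at random within each location stratum.
2. Delete the block sizes from Sections 5 and 6.1, stating only that permuted blocks of varying size are used within strata. Record the new sizes in a document held only by the statistician.

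Deletion alone would not help with staff who have already read the current sizes, so a new list is needed. A new list with published sizes would leave most of the modelled bias.

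The cost is a protocol amendment, a new list in the randomization software, and slightly larger expected arm imbalance. Section 6.2 says that the process will ensure equal numbers by location on each arm; neither scheme guarantees exact equality, so that sentence could be softened in the same amendment. Allocations already made are not helped.
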